4.4.2. Vaccine and Exposure to Infections Guidelines

4.4.2.1. Subject Specific Recommendations

It is recommended that all subjects should be up-to-date with respect to standard of care vaccinations (as defined by their country health ministry) or AD guidelines. Vaccination of subjects with live components is prohibited within the 6 weeks prior to first dose of investigational product. Adolescent subjects without documented evidence of having received at least one dose of the varicella vaccine or those who are without evidence of previous varicella zoster exposure as confirmed by VZV IgG Ab serological testing are excluded.

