- b. Female subjects of childbearing potential ≥ 15 years of age who are at risk of pregnancy must agree to use a highly effective method of contraception (as per [Section 4.4.1](#)) for the duration of the active treatment period and for at least 28 days after the last dose of investigational product;
- c. Female subjects less than 15 years of age must not be sexually active, and abstinence per the below definition should be confirmed prior to enrollment.

NOTE: Sexual abstinence, defined as completely and persistently refraining from all heterosexual intercourse (including during the entire period of risk associated with study treatments) may obviate the need for contraception ONLY if this is the preferred and usual lifestyle of the subject.

6. Female subjects of non-childbearing potential must meet at least 1 of the following criteria:
 - Have undergone a documented hysterectomy and/or bilateral oophorectomy;
 - Have medically confirmed ovarian failure; or
 - Achieved postmenopausal status, defined as follows: cessation of regular menses for at least 12 consecutive months with no alternative pathological or physiological cause and have a serum follicle-stimulating hormone (FSH) level confirming the postmenopausal state.

All other female subjects (including female subjects with tubal ligations) are considered to be of childbearing potential.

7. Must agree to avoid prolonged exposure to the sun and not to use tanning booths, sun lamps or other ultraviolet light sources during the study.
8. If receiving concomitant medications for any reason other than AD, must be on a stable regimen, which is defined as not starting a new drug or changing dosage within 7 days or 5 half-lives (whichever is longer) prior to Day 1 and through the duration of the study.

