4.2. Exclusion Criteria

Subjects with any of the following characteristics/conditions will not be included in the study:

1. Other acute or chronic medical or psychiatric condition including recent (within the past year) or active suicidal ideation or behavior or laboratory abnormality that may increase the risk associated with study participation or investigational product administration or may interfere with the interpretation of study results and, in the judgment of the investigator, would make the subject inappropriate for entry into this study.
2. Any psychiatric condition including recent or active suicidal ideation or behavior that meets any of the following criteria:
 - Suicidal ideation associated with actual intent and a method or plan in the past year: “Yes” answers on items 4 or 5 of the Columbia suicide severity rating scale (C-SSRS) (Appendix 15);
 - Previous history of suicidal behaviors in the past 5 years: “Yes” answer (for events that occurred in the past 5 years) to any of the suicidal behavior items of the C-SSRS;
 - Any lifetime history of serious or recurrent suicidal behavior;

- Suicidal behaviors questionnaire – revised (SBQ-R) total score ≥ 8 (Appendix 16);
 - Clinically significant depression: patient health questionnaire – 8 items (PHQ-8) total score ≥ 15 (Appendix 17);
 - The presence of any current major psychiatric disorder that is not explicitly permitted in the inclusion/exclusion criteria;
 - In the opinion of the investigator or Pfizer (or designee) exclusion is required.
3. A current or past medical history of conditions associated with thrombocytopenia, coagulopathy or platelet dysfunction.
 4. Receiving anti-coagulants or medications known to cause thrombocytopenia, (unless considered safe to stop and washout for the duration of the study).
 5. Currently have active forms of other inflammatory skin diseases, ie, not AD or have evidence of skin conditions (eg, psoriasis, seborrheic dermatitis, Lupus) at the time of Day 1 that would interfere with evaluation of atopic dermatitis or response to treatment.
 6. Vaccinated or exposed to a live or attenuated vaccine within the 6 weeks prior to the first dose of investigational product, or is expected to be vaccinated or to have household exposure to these vaccines during treatment or during the 6 weeks following discontinuation of investigational product.

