4.4. Lifestyle Requirements

In order to participate in the study, subjects must be aware of the following lifestyle guidelines and restrictions that apply during and after the treatment period.

- On study visit days (Day 1, Weeks 4, 12 and End of Study [EOS]), subjects must comply with fasting requirement for at least 8 hours prior to the visit. Water and permitted non-study medications are allowed (see [Section 5.8.1](#)).

- On study visit days, subjects must not smoke or ingest caffeine during the 30 minutes prior to blood pressure and heart rate measurements.
- On study visit days, subjects must not take the dose of investigational product until instructed to do so by the investigator or designated study site staff.
- On study visit days, showering or bathing is permitted prior to attending the study visit, but subjects must not moisturize or apply emollient. Non-medicated emollient is allowed after the visit. Discontinue and avoid using certain medications and treatments ([Section 4.2](#), [Section 5.8.2](#), and Appendix 3).
- Agree to use one highly effective method of contraception (as specified in [Section 4.4.1](#), as applicable).

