4.4.1. Contraception

All female subjects who are of childbearing potential which includes all female subjects aged 12 years and older, regardless of whether they have experienced menarche, who are, in the opinion of the investigator, sexually active and at risk for pregnancy with their partner(s) must agree to use a highly effective method of contraception consistently and correctly for the duration of the active treatment period and for at least 28 days after the last dose of investigational product.

For Czech Republic only, the contraception paragraph above is revised to require:

Female subjects less than 15 years of age must be abstinent from sexual activity in order to participate in the study. All other female subjects of childbearing potential, regardless of whether they have experienced menarche, who are, in the opinion of the investigator, sexually active and at risk for pregnancy with their partner(s) must agree to use a highly effective method of contraception consistently and correctly for the duration of the active treatment period and for at least 28 days after the last dose of investigational product.

The investigator or his or her designee, in consultation with the subject, will confirm that the subject has selected an appropriate method of contraception for the individual subject and her partner from the permitted list of contraception methods (see below) and will confirm that the subject has been instructed in its consistent and correct use. At time points indicated in the [Schedule of Activities](#), the investigator or designee will inform the subject of the need to use highly effective contraception consistently and correctly and document the conversation and the subject's affirmation in the subject's chart (subjects needs to affirm their consistent and correct use of at least 1 of the selected methods of contraception). In addition, the investigator or designee will instruct the subject to call immediately if the selected contraception method is discontinued or if pregnancy is known or suspected in the subject or the partner.

Highly effective methods of contraception are those that, alone or in combination, result in a failure rate of less than 1% per year when used consistently and correctly (ie, perfect use) and include the following:

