5.8. Concomitant Treatment(s)

Subjects will abstain from all concomitant medications as described in [Section 4.2](#) and Appendix 3 of the protocol. Medications that are taken in the Screening/Washout period (after informed consent is obtained and before the first dose of investigational product) will be documented as prior medications. Medications taken after the first dose of investigational product has been administered will be documented as concomitant medications. All concomitant medications taken during the study must be recorded in study records with indication (if atopic dermatitis), reference to any associated adverse event, dose, and start and

stop dates of administration. Subjects will be queried about concomitant medication (including topical medications and treatments, over-the-counter and prescription medications and treatments, and vaccinations) at each study visit. Any new concomitant medications or dose changes to current concomitant medications should be evaluated for potential new or worsening adverse events.

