5.8.2. Prohibited Medications and Treatments

Subjects are required to discontinue and avoid using certain medications and treatments (see [Section 4.2](#), Inclusion Criteria and Exclusion Criteria, and Appendix 3). Subjects should be instructed at each visit to contact the study site investigator promptly if there are any intended changes or additions to concomitant medications.

All medications and treatments that could affect atopic dermatitis must be discontinued except oral antihistamines. Due to the potential to affect atopic dermatitis with ultraviolet light exposure, subjects must also avoid prolonged exposure to the sun and not to use tanning booths, sun lamps or other ultraviolet light sources during the study.

Subjects who received prior treatment with JAK inhibitors are to be excluded from the study.

Herbal medications with unknown properties or known beneficial effects for AD must be discontinued at least 4 weeks before the first dose of investigational product.

Restrictions on certain vaccinations are described in [Section 4.4.2](#).

The Pfizer study team is to be notified of any prohibited medications taken during the study. After consulting with the Medical Monitor, the investigator will make a judgement on the ongoing eligibility of any subject with prohibited medication use during the study.

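### Section 4.4.2.1 bans the subject's own live vaccination only before first dose; the on-treatment and 6-week post-treatment period is stated only in exclusion criterion 6, as an expectation at entry

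*Protocol*

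**What the plan says.** Protocol 4.4 introduces its contents as "lifestyle guidelines and restrictions that apply during and after the treatment period". Within it, 4.4.2.1 deals with the subject's own vaccination. It opens with general advice, "It is recommended that all subjects should be up-to-date with respect to standard of care vaccinations", and then gives its one rule on live vaccines: "Vaccination of subjects with live components is prohibited within the 6 weeks prior to first dose of investigational product". Its remaining sentence repeats the varicella entry requirement for adolescents. Section 4.4.2.2 concerns contact with other people who have been vaccinated.

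Section 5.8.2, on prohibited treatments, says "Restrictions on certain vaccinations are described in" section 4.4.2.

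Exclusion criterion 6 in section 4.2 has the longer period. Besides barring recent live vaccination, it excludes a subject who is "expected to be vaccinated or to have household exposure to these vaccines during treatment or during the 6 weeks following discontinuation of investigational product".

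Section 5.8 requires abstention from the concomitant medications described in section 4.2 and Appendix 3. It also has subjects asked about concomitant medication, with a bracketed list that ends "over-the-counter and prescription medications and treatments, and vaccinations) at each study visit".

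**The concern.** Criterion 6 is applied once, at entry, to what is then expected. A subject with no vaccination planned at that point satisfies it, even if one is offered in Week 6 or soon after the last dose. The section that site staff consult during the study should then carry the rule, but 4.4.2.1 stops at first dose. The sentence before its ban recommends keeping vaccinations current and makes no exception for live vaccines once dosing has begun.

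A subject could therefore receive a live vaccine while taking a JAK1 inhibitor, or shortly after stopping, without departing from anything 4.4.2.1 says. Section 1.4 lists viral reactivation and serious and opportunistic infections among the potential risks. Staff are also asked at every visit (sections 6.1 to 6.3.1) to assess adherence to the section 4.4 requirements, and on this subject 4.4.2.1 gives them nothing to check after Day 1.

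**Working it through.** The plan gives no figure to reproduce. The check is a comparison of the text, followed by day counts.

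**Where the subject's own live vaccination is restricted**

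- *4.4.2.1:* explicit ban, 6 weeks before first dose only.
- *4.4.2.2:* contact with vaccinated others; silent on vaccinating the subject.
- *Criterion 6:* names the vaccines and the full period, but as an entry expectation.
- *5.8:* abstention by reference to 4.2; vaccinations counted as concomitant medication and asked about; live vaccines not named.
- *4.4 and 5.8.2:* general references to 4.2 for medications and treatments to avoid.
- *Inclusion criterion 8:* "If receiving concomitant medications for any reason other than AD, must be on a stable regimen" through the study; vaccines not named.
- *5.8.1:* additions after Day 1 limited to what is medically essential.
- *5.8.2:* subjects to report intended additions to the investigator.
- *Appendix 3:* CYP inhibitors and inducers only. *Appendix 4:* no vaccine rule.

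The neighbouring section 4.4.1 shows the alternative drafting. Inclusion criterion 5b already sets the contraception period, yet 4.4.1 restates it in full: "for the duration of the active treatment period and for at least 28 days after the last dose of investigational product".

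**Length of the period not stated in 4.4.2.1**

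Inputs: first dose on Day 1; Week 12 visit on Day 85 ± 3 with dosing in clinic (6.2.7), so a completer's last dose L is Day 82 to 88; 6 weeks = 42 days. Discontinuation is taken as the day of last dose.

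- End of criterion 6's period = L + 42: 82 + 42 = Day 124; 85 + 42 = Day 127; 88 + 42 = Day 130.
- Whole period = 42 days before Day 1, plus Day 1 to that date: 42 + 124 = 166; 42 + 127 = 169; 42 + 130 = 172 days.
- Share stated in 4.4.2.1: 42/166 = 25.3%; 42/169 = 24.9%; 42/172 = 24.4%.

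**How far the period runs past the last visit (subjects in follow-up)**

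Days from Visit 9 to the end of the period = 42 − (Visit 9 − L).

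- Completer, Visit 9 at 28 ± 3 days after end of treatment: Visit 9 − L is 25 to 31, leaving 42 − 31 = 11 to 42 − 25 = 17 days.
- Completer, Visit 9 at Day 120 ± 3 (the 6.3.1 heading): Visit 9 − L is 117 − 88 = 29 to 123 − 82 = 41, leaving 42 − 41 = 1 to 42 − 29 = 13 days.
- Early stopper, end-of-treatment visit up to 7 days after last dose (6.4): Visit 9 − L is 25 to 7 + 31 = 38, leaving 42 − 38 = 4 to 42 − 25 = 17 days.

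So the period ends 1 to 17 days after Visit 9 if windows are kept. Subjects entering the extension study have no Visit 9 here and are outside these figures.

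**The case against.** The strongest reply is that the protocol does restrict live vaccination on study. Section 5.8 treats vaccinations as concomitant medication, and its opening sentence has subjects abstain as described in section 4.2, which contains criterion 6. Sections 4.4 and 5.8.2 point to 4.2 as well. Sections 5.8.1 and 5.8.2 limit additions and ask that they be reported. Section 4.4.2.2 warns even about second-hand exposure on treatment, so a site is unlikely to conclude that vaccinating the subject is acceptable. Criterion 6 also removes at entry anyone with a vaccination expected.

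Most of this stands. A reader might infer that the protocol permits live vaccination during treatment, or has no on-study restriction at all. The documents do not support that: the intent is plain, and an indirect restriction can be assembled from 5.8 and 4.2. But that route ends in an eligibility criterion worded as an expectation, and it does not correct the shorter ban in the section 5.8.2 cites specifically for vaccination. The general limits do not name live vaccines or give the 6 weeks after stopping. Repeating a period, as 4.4.1 does, is partly a matter of drafting style, so that contrast is supporting evidence only.

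A reader might also see a second inconsistency. For household contact, criterion 6 counts 6 weeks from discontinuation of product, whereas 4.4.2.2 counts from completion of the study. For subjects in follow-up the 4.4.2.2 date is later by Visit 9 − L, which is 25 to 41 days across the cases above. This should not be pressed as a fault. Section 4.4.2.2 is guidance, criterion 6 is an entry screen, and the longer period errs toward caution. Aligning the two on discontinuation would shorten a precaution by 25 to 41 days with no safety gain.

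**Conclusion.** The point holds as a drafting gap with a bearing on safety. The section sites are sent to for vaccination restrictions states about a quarter of the period that criterion 6 shows was intended for the subject's own live vaccination: 42 of about 169 days for a completer (166 to 172 with the visit window). From Day 1 to about Day 127 the restriction has to be inferred from other sections.

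The day counts assume that discontinuation means the day of last dose and that visit windows are kept. What applies to extension entrants after Week 12 depends on a protocol not among these documents. The share measures coverage of the text; nothing in the documents shows that any subject was vaccinated or harmed. Power, type I error and the planned analyses are untouched. The change is worth making because the drug is an immunomodulator with listed infection risks and the correction is small.

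**What to change.** In 4.4.2.1, state that live or attenuated vaccination of the subject is prohibited from 6 weeks before first dose, throughout treatment, and for 6 weeks after discontinuation of investigational product. This is criterion 6's own period, so no new policy is introduced. Leave the household-contact wording in 4.4.2.2 unchanged.

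The cost is one sentence in a protocol amendment and one added explicit instruction to sites and subjects. For subjects in follow-up that instruction has to be given by Visit 9, because the period ends 1 to 17 days after it. No visit, test or analysis is added.

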4.4.2.2. Guidance Regarding Household Contact Vaccine-Related Exposure

Current routine household contact with children and others who have been vaccinated with live vaccine components may pose a risk during treatment and for 6 weeks following completion of the study. Some of these vaccines include varicella ("chickenpox") vaccine, oral polio vaccine, and the inhaled flu vaccine. Following vaccination with live component vaccines, the virus may be shed in bodily fluids, including stool, and there is a potential risk that the virus may be transmitted. General guidelines for immunosuppressed subjects suggest that exposure (through routine contact) should be avoided following vaccination (of others) with these vaccines for the stated time period:

- a. Varicella or attenuated typhoid fever vaccination for 4 weeks following vaccination.
- b. Oral polio vaccination for 6 weeks following vaccination.
- c. Attenuated rotavirus vaccine for 10 days following vaccination.
- d. FluMist® (inhaled flu vaccine) for 1 week following vaccination.

Subjects should avoid exposure to vaccinated or infected persons and contact the investigator promptly should they develop signs or symptoms of infections.

4.4.3. Surgery

During the study, no elective surgery should occur without first consulting with the Pfizer Medical Monitor or designee. Preferably, elective surgery should occur before the study or be delayed until participation in the study is completed.

The Pfizer Medical Monitor or designee should be notified if a subject requires surgery (including dental surgery) during the study to determine whether the subject should discontinue from the study and/or discontinue investigational product prior to the surgical procedure. In general, planned surgical procedures should not be performed unless the investigational product has been discontinued for at least 28 days (unless otherwise advised by the Pfizer Medical Monitor or designee). The Pfizer Medical Monitor or designee should be notified as soon as possible if a subject undergoes a surgical procedure without first informing the study staff.

4.5. Sponsor's Qualified Medical Personnel

The contact information for the sponsor's appropriately qualified medical personnel for the study is documented in the study contact list located in the coordinator's manual and in the study portal.

To facilitate access to appropriately qualified medical personnel on study-related medical questions or problems, subjects are provided with a contact card. The contact card contains, at a minimum, protocol and investigational product identifiers, subject study numbers, contact information for the investigator site, and contact details for a contact center in the event that the investigator site staff cannot be reached to provide advice on a medical question or problem originating from another healthcare professional not involved in the subject's participation in the study. The contact number can also be used by investigator staff if they are seeking advice on medical questions or problems; however, it should be used only in the event that the established communication pathways between the investigator site and the study team are not available. It is therefore intended to augment, but not replace, the established communication pathways between the investigator site and the study team for advice on medical questions or problems that may arise during the study. The contact number is not intended for use by the subject directly, and if a subject or their parent(s)/legal guardian calls that number, he or she will be directed back to the investigator site.

5. STUDY TREATMENTS

For this study, the investigational products are PF-04965842 and placebo. PF-04965842 will be administered orally at doses of 100 mg or 200 mg given QD for 12 weeks based on treatment assignment. In addition, one treatment group will be assigned to receive PF-04965842-matching placebo.

For the purposes of this study, and per International Conference on Harmonisation (ICH) guidelines, investigational product is defined as a pharmaceutical form of an active ingredient or placebo being tested or used as a reference/comparator in a clinical trial, including a product with a marketing authorization when used or assembled (formulated or packaged) in a way different from the approved form, or when used for an unapproved indication, or when used to gain further information about an approved use (ICH E6 1.33).

5.1. Allocation to Treatment

Allocation of subjects to treatment groups will proceed through the use of an Interactive Response Technology (IRT) system. The site personnel (study coordinator or specified designee) will be required to enter or select information including but not limited to the user's identification (ID) and password, protocol number, the subject number and the date of birth of the subject. The site personnel will then be provided with a treatment assignment and dispensable unit (DU) or container number when investigational product is being supplied via the IRT. The IRT system will provide a confirmation report containing the subject number and DU or container number assigned. The confirmation report must be stored in the site's files.

There is a 24 hour a day, 365 days a year IRT help desk available for any questions or issues. The study specific IRT reference manual will provide the contact information and further details on the use of the IRT.

Note: The IRT is the source of the subject number. The IRT system will provide the subject number at the end of the first IRT subject transaction.

